A 4-arm randomized controlled trial of Fuse, EndoCuff, EndoRings and standard colonoscopy for improving adenoma detection rates.

Protocol:

Introduction:

ADR (Adenoma detection rate or percentage of patients with at least one adenoma among all colonoscopies performed by a doctor) was first proposed as a quality indicator 12 years ago. It has now been validated as an excellent marker for the risk of interval colorectal cancer (cancer occurring after colonoscopy). Although colonoscopy offers protection from colorectal cancer for at least a decade and more, this protection has been shown to vary depending on the location and type of pre-cancerous lesions and the training and skill of the doctor performing the procedure. A recent large study of more than 200,000 colonoscopies found that every 1% increase in ADR resulted in a decrease of interval CRC by 3% and fatal interval CRC by 5%. Although the increase was linear the effect was more pronounced once the ADR reaches 28% and continued beyond till 52%.

Measures to improve ADR are therefore a worthy goal to study. Recent studies indicate that continuing medical education, time of colonoscopy during the day, forced longer withdrawal time, use of high definition colonoscopes all result in improving ADR although the gains have only been modest. To this end, adding novel devices to the tip of colonoscope may improve the ability of doctors to perform a better procedure. We therefore propose to identify the increase in ADR with 3 of these devices compared to standard colonoscopy. Fuse colonoscopy (2 cameras embedded at the side of the colonoscope tip providing an increased angle of view), EndoCuff (a plastic cap to fit the tip with flexible arms which hold the mucosa back aiding in inspection), EndoRings (similar to EndoCuff but the arms are wider) have been shown in tandem colonoscopy studies to improve the adenoma miss rates to 7-15%

instead of the miss rates seen with standard colonoscopy which is usually about 40%. All these devices are FDA approved and are distributed in the United States.

Methods:

Persons scheduled for a standard screening, surveillance or diagnostic colonoscopy at the Glen Lehman Endoscopy Suite will be invited to participate in the study after a member of the research team explains the risks, benefits and the choice of not participating in research.

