If the patient qualifies after being screened for exclusion criteria as listed below, they will be given an informed consent document and an authorized HIPAA form to sign. Once both documents are signed, a copy will be provided to the patient and then the patient is randomized to undergo a standard colonoscopy, a Fuse colonoscopy, colonoscopy with EndoCuff or a colonoscopy with EndoRings.

Study procedures:

Patients will undergo a split dose bowel preparation starting the evening before the procedure day and ending at least 4 hrs. prior to the procedure. Patients with medical indicators of inadequate bowel preparation are given a more intensive regimen sometimes doubling the dose of preparation drug. Patients agreeing to participate will be randomized to one of the four study arms prior to initiation of colonoscopy.

A colonoscope will be introduced and advanced to the cecum at which time a research assistant will note the time taken to achieve this. Once the withdrawal starts, the same assistant will start a stopwatch which will be stopped for any cleaning of the bowel or polypectomy procedures. In this way inspection time can be monitored for all arms of the study.

After randomization, a patient can be withdrawn due to condition discovered during colonoscopy which places the patient in the exclusion criteria, an inadequate bowel preparation as determined by the performing doctor or a request from the patient to be withdrawn.

Inclusion criteria:

Screening colonoscopy, Surveillance colonoscopy or diagnostic colonoscopy and ≥ 50 years of age

Exclusion criteria:

Any personal h/o large bowel resection, inflammatory bowel disease, or polyposis syndromes

Any family h/o polyposis syndromes

Referral for an incomplete exam or polyp clearance

Referral for a FOBT+ testing in the last 6 months

Anticipated difficult colonoscopy

Statistical analyses:

We will perform analyses on the data after randomization and prior to withdrawal (intention to treat) and on data of patients completing the study (excluding the withdrawal patients, per protocol).

The primary aim of increased ADR detection will be tested using a chi-square test among the four groups.

The secondary aims of cecal intubation rates, cecal insertion time and detection of serrated and flat lesions will be tested using chi-square, t-test, and chi-square respectively.

All analyses will be performed on SPSS Version 20 (IBM, NY).

Sample size:

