The ADR of the principal investigator has averaged about 40% in published studies. We hope to achieve a 10% increase in the ADR with these newer devices when compared to standard colonoscopy.

Using a 4-arm RCT, to detect a 10% increase from a baseline of 40%, we require 388 patients in each arm at an α level of 0.05 with 80% power (n=1552). To account for the withdrawals after randomization, which would amount to an average of 6% per our recent studies, we will need to enroll 412 patients in each arm (n=1648).

Ethical considerations:

All protocols will be approved by the local IRB before starting the research study. An informed consent document will be provided to each patient to review for participating in the study. An express authorization to review medical data for research purposes will be obtained before randomizing any patient. All patients will be provided with a contact number in case of questions or if they wish to inform of their intent to be withdrawn.

Adverse events:

The primary investigator will monitor any adverse event reported to the study staff and determine if it's related to the study procedures including standard colonoscopy. All adverse events will be monitored until a satisfactory resolution and will be reported to the IRB within 5 days of knowledge.

A table will be maintained for the adverse events in each arm and in case of any statistically significant adverse event rate in any arm, the primary investigator will make the decision to remove the treatment arm or stop the study.

Data integrity and safety:

All paper charts pertaining to the patient will be kept under lock and key in coordinators office away from the endoscopy area. The data entry will be performed into an excel file which will be stored on an internal network drive with encryption and password security. Only approved personnel by the IRB will have access to the file storage. This file will also not have any identifiable information (name, DOB or mrn). A study log with the identifiable information will be kept in a separate folder (also encrypted) to enable the investigators to assist in any research audit. No procedural data except the date of examination will be entered into this log.

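### The primary ADR test is a crude four-group chi-square; prespecified adjustment for indication and age is an optional, low-cost gain in precision of unknown and possibly zero size

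*Combined protocol and SAP*

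**What the plan says.** The Statistical analyses section states: "The primary aim of increased ADR detection will be tested using a chi-square test among the four groups". That is the only analysis given for ADR. It is to be run on an intention-to-treat set and a per-protocol set, and no covariate, regression model or stratified test is named for either.

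On allocation, Study procedures says: "Patients agreeing to participate will be randomized to one of the four study arms prior to initiation of colonoscopy". No stratification factor is described. That silence does not show that none was used.

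The Inclusion criteria read: "Screening colonoscopy, Surveillance colonoscopy or diagnostic colonoscopy and ≥ 50 years of age". Three indications and an open-ended age range are therefore mixed in one trial, and both variables are established before allocation.

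The Introduction says that "time of colonoscopy during the day, forced longer withdrawal time, use of high definition colonoscopes all result in improving ADR", while calling the gains modest. Time of day does not reappear in the analysis plan.

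Under Sample size, the only baseline rate is an overall one: "The ADR of the principal investigator has averaged about 40% in published studies". No ADR by indication or by age appears anywhere, and neither does the expected mix of indications.

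**The concern.** A four-arm trial that enrols screening, surveillance and diagnostic patients from age 50 upward may contain patients with quite different chances of having an adenoma detected. If so, part of the variation in the outcome can be explained by variables fixed before allocation. A crude chi-square leaves that variation in the error term. A model that includes those variables would estimate the device effects more precisely without enrolling anyone else.

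An opportunity is at stake here, not validity. The crude test keeps its type I error rate, and chance imbalance between arms is already reflected in its standard error. Adjustment that is not written down beforehand could, however, be chosen after the results are seen, and would then carry little weight.

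The Introduction's aim is to measure the rise in ADR with each of three devices against standard colonoscopy. A four-group test alone gives no such estimate, so the plan would benefit from prespecified risk differences in any case.

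**Working it through.** **Inputs from the Sample size section.** Control ADR 40%; increase of 10%, read as absolute (40% v 50%); α 0.05; power 80%; 388 per arm (1552 in total); 412 per arm enrolled (1648) to allow for 6% withdrawals.

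**Reproducing the plan's figure.** Two-sided comparison of two proportions, pooled variance under the null, no continuity correction:

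n = [1.96·√(2·0.45·0.55) + 0.8416·√(0.24 + 0.25)]² / 0.10² = (1.3790 + 0.5891)² / 0.01 = 387.3, so 388 per arm.

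This matches the plan. Reading the increase as relative (40% v 44%) would need 2389 per arm, so the absolute reading is the one used. 388 × 1.06 = 411.3, rounded up to 412.

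**Power of the planned crude test at 388 per arm.** With all three devices at 50%, mean ADR is 0.475 and the 3-df noncentrality is

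388·[(0.075)² + 3·(0.025)²] / (0.475·0.525) = 388·0.0075/0.249375 = 11.67,

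which gives 82.9% power. If only one device reaches 50%, power is 83.7%. Pairwise power is 80.1%. The 95% CI half-width for one device v standard is 1.96·√((0.24 + 0.25)/388) = 6.97 points. At 412 per arm, which applies if the intention-to-treat set keeps nearly everyone enrolled, these become 85.3% (all three devices at 50%), 82.4% (pairwise) and 6.76 points.

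**Gain from adjustment.** With mix w and ADR p by indication, R² = Σ w(p − p̄)² / [p̄(1 − p̄)]. Adjustment then acts roughly like a sample of n/(1 − R²). Every mix, ADR by indication and age effect below is an assumption. Worked example for 35/55/25% with mix 40/40/20: p̄ = 0.41; Σ = 0.4·0.06² + 0.4·0.14² + 0.2·0.16² = 0.0144; R² = 0.0144/(0.41·0.59) = 0.060.

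| Assumed ADR: screening/surveillance/diagnostic (mix) | R² | Effective n for 388 | Pairwise power | 3-df power (all devices 50%) |
|---|---|---|---|---|
| No link | 0 | 388 | 80.1% | 82.9% |
| 39/42/39% (50/30/20) | 0.001 | 388 | 80.1% | 82.9% |
| 38/45/33% (40/40/20) | 0.009 | 392 | 80.4% | 83.3% |
| 35/50/30% (40/40/20) | 0.029 | 400 | 81.2% | 84.1% |
| 35/55/25% (40/40/20) | 0.060 | 413 | 82.4% | 85.3% |
| As above plus age (mean 63, SD 7, OR 1.7 per 10 years) | 0.082 | 423 | 83.3% | 86.3% |

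In the last row the half-width falls to 6.67 points, and power with only one device at 50% rises to 87.0%. The equivalent saving is 388/0.918 − 388 ≈ 35 per arm, or about 139 over four arms. At 412 per arm the same R² gives 85.5% pairwise, 88.4% for 3 df, and 6.48 points.

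**Chance imbalance.** The 95% range of the ADR difference between two arms that arises from imbalance in indication alone is 1.96·√(2·Var(p)/388), where Var(p) is the Σ above. Down the five indication-only rows this is 0, 0.19, 0.65, 1.18 and 1.69 points. With the assumed age effect it is about 2.0 points.

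**Simulation check** (388 per arm, logistic model with indication and age, 4000 to 6000 runs). Adjusted minus crude 3-df power:
- no link: +0.1 points (SE 0.15)
- 39/42/39%: 0.0
- 38/45/33%: +0.5 (SE 0.23)
- 35/50/30% with age OR 1.25: +1.4 to +2.2 (SE 0.3)
- 35/55/25% with age OR 1.7: +3.6 to +3.8 (SE 0.3 to 0.4)

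Type I error over seven null runs of 4000 was 4.5 to 5.6% crude and 4.6 to 5.5% adjusted (Monte Carlo SE 0.34). The standardised risk difference averaged 9.9 to 10.1 points against a true 10. In the strongest scenario its SD was 3.4, against 3.5 to 3.6 crude.

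A separate set of 1500 runs per setting, with only one device at 50%, gave 83.9% crude v 84.0% adjusted at R² = 0, and 84.0% v 86.9% at R² of about 0.07. A more extreme R² of about 0.14, beyond the table, gave 83.7% v 88.9%.

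**The case against.** The strongest reply is that nothing is wrong with the plan. The crude test is valid, the sample size was built on crude proportions, and the two agree on this point. The documents do not say that indication or age predicts ADR. The one pre-procedure patient-level factor that they do link to ADR, time of day, is not sized here. The top of the range needs a 30-point spread in ADR between indications (55% v 25%) plus a strong age effect, and the milder scenarios gain half a point or nothing. Even at the top, the half-width shrinks by only 0.30 points. Adjustment also brings choices of its own: the functional form for age, the handling of missing covariates, and a test on the log-odds scale that could disagree near the 5% boundary with intervals on the risk-difference scale.

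Most of this stands. The gain is unknown and may be zero, and the patient-equivalent figure should not be read as an expected saving. It does not defeat the suggestion. The covariates are already in hand, an uninformative covariate costs almost nothing with some 1550 patients, and the modelling choices can be settled in a few lines of SAP text. Keeping the chi-square as primary, with the adjusted analysis prespecified alongside it, would also be defensible. It would give the tighter intervals but not the added power for the primary test.

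**Conclusion.** The point holds as an optional improvement, not as a fault. The plan's primary analysis is unadjusted, and the documents describe neither stratification nor adjustment, although two plausible prognostic variables are known for every patient before allocation. The benefit of using them cannot be sized from the documents. Over assumed R² values of 0 to 0.082 it is 0 to about 3 or 4 percentage points of power and 0 to 0.30 points of CI half-width at 388 per arm. The trial does not depend on it, since crude four-group power is already 82.9% at 388 and 85.3% at 412 if all three devices reach 50%. The sample size should not be reduced on the strength of an assumed R².

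Multiplicity across the three device comparisons, and the use of a pairwise calculation to size a four-group test, are separate matters that this does not settle.

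**What to change.** Before outcome data are examined, add to the SAP:

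- A logistic regression of adenoma detection (yes/no) on arm, indication (three levels) and age in years, with a 3-df test of arm as the primary test. State the form in which age enters and how a missing covariate is handled.
- Covariate-standardised risk differences with 95% CIs for each device v standard, by delta method or bootstrap, so that the effect stays on the ADR scale.
- Any factor used to stratify the randomization, if there was one. Scheduled time of day may be added if it is fixed before randomization.
- No adjustment for withdrawal or inspection time. It is measured after randomization and the device may affect it.
- Crude proportions and the four-group chi-square, kept as supportive.

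The cost is low but not nil. It needs SAP wording and a standardisation step; the team should confirm that the named package, SPSS Version 20, can do this or name another. Indication and age in years must be entered deliberately, because Data integrity and safety says the data file holds no date of birth. No extra patients or visits are needed.
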